Study Schema: Controlled, randomized, double-blind, prospective, parallel-group, intent-to-treat **Aim 1** clinical trial to test the efficacy of three energy doses [0.6, 1.0, and 1.3 x measured REE (MREE), by metabolic cart, respectively], given for 28 consecutive days during the ICU and post-ICU course in critically ill medical and surgical patients requiring parenteral nutrition (PN) ±enteral nutrition (EN) at Emory University. The primary endpoint is total hospital-acquired infections after entry; secondary endpoints are bloodstream infections, ventilator-free days, and ICU and 28-day hospital length of stay and mortality. **Aim 2** examines the effect of cumulative and mean daily measured 28-day energy deficits after entry on Aim 1 clinical outcome endpoints and relationships between estimated REE (Harris-Benedict equation) at study entry. **Aim 3** explores the impact of energy dose and cumulative and mean daily 28-day energy deficits on global metabolomic patterns, microbiome, and strength over time and in association with key clinical outcomes in Aim 1.

↑ Plasma (metabolome), microbiome, and strength analysis

Data Collection: Baseline data collected will include APACHE II score, and clinical and demographic data. The following will be collected during the course of the study:

A) Measured resting energy expenditure (MREE; per metabolic cart) will be determined on the baseline day before 2 pm. The goal energy dose composition of PN for all three energy doses for each enrolled subject is calculated by the blinded research team members. The metabolic cart-derived REE will be used to determine basal energy expenditure (REE) and thus the initial energy dosing^{5, 10, 12}. MREE will be determined at baseline and 5x weekly (M-F before 2 pm; see Aim 2) using a state-of-the-art metabolic

cart and standard methodologies by a study team respiratory technician with prior experience and expertise in clinical indirect calorimetry. In the event that the metabolic cart is not available, the most recent measurements will be used. The nutrition will not be adjusted if the MREE is <10% changed from the reading the day before.

- B) Longitudinal SOFA scores of organ dysfunction/failure: Sequential organ failure assessment (SOFA) scores will be calculated in the morning of each ICU day ⁶⁰. The baseline Apache II score on the day of ICU admission will also be calculated in all patients.

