standardized CRFs. The primary endpoint is total nosocomial infection rate during the 28-day study period. Secondary Aim 1 post-entry endpoints to be monitored include: 1) 28-day hospital mortality; 2) Rate of new nosocomial blood stream infections (BSIs) during the initial 28 days; 3) Rate of new nosocomial infections during the initial 28 days; 4) mean ICU SOFA score; 5) ICU ventilator-free days at day 28; 6) ICU and total hospital length of stay.

Hospital nutrition support - Administration of double blind parenteral and enteral nutrition:

Briefly, the nutritional goals are to provide total daily calorie (kcal) intake [from PN + dextrose-containing IV fluids (> 500 mL/day) + propofol/clevidipine + any enteral feedings) at 0.6, 1.0 or 1.3 x baseline MEE (per metabolic cart). We will then serially adjust total PN/EN energy dosing based on real-time serial cart REE measurements during the ICU stay, as indicated by the energy dose group to which the patient is randomized. The total amino acid/protein intake goal is 1.2 g/kg/day. Dextrose will initially comprise 70% of PN non-amino acid kcal and IV fat (30% Intralipid[®]) 30% of PN non-amino acid kcal daily, adjusted as clinically indicated. The 1.0 x REE energy dose study group will serve as the control group in this CER study. Study PN will be continued only if deemed indicated by the investigators and the primary physicians. Daily intake of study PN volume (mL), PN dextrose (g), PN lipid emulsion (g), intake of study tube feeding volume, and daily PN and enteral (oral or tube feeding) volumes will be calculated and entered into the CRFs daily for the initial 28 days after entry, beginning on day 1.

Study subjects will receive a maximum of 28 days of double blind study PN ± EN. Subjects will be transitioned from PN to enteral feeds as soon as tolerated and clinically indicated. Study PN will be discontinued when enteral intake of \geq 50% of energy requirements is achieved for \geq 48 hr. The amount of PN administered will be decreased as a function of actual enteral nutrient intake to maintain daily goals. The 24-hr daily study PN will be prepared under sterile laminar air flow hood conditions by the unblinded research pharmacist and pharmacy technician at each site. The study EN will be made in the Metabolic Kitchen or in the compounding area of the pharmacy.

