gut microbiota in all fecal samples will be identified using established next generation DNA sequencing of 16S rRNA libraries, performed by our collaborator [name] of the University of Chicago (6, 18, 66). Briefly, 50 mg of frozen fecal sample will be homogenized in extraction buffer and 0.1-mm-diameter zirconia/silica beads are added prior to lysing of microbial cells on a Mini-Beadbeater-8 cell disrupter. After overnight incubation at 55°C, extraction with phenol: chloroform: isoamyl alcohol, and precipitation with ethanol will be performed. Isolated DNA is dissolved in Tris-EDTA buffer and stored at -80°C. The 16S rRNA gene sequences are amplified from DNA samples using barcode-labeled primers for the V3–V4 region of the 16S rRNA encoding gene (*Escherichia coli* positions 338–806), as outlined^{65–67}. The Shannon diversity index and distinctive peak numbers (richness) of the OTUs in the microbiome libraries between baseline (day 0) and serial fecal samples (days 3, 7, and 14) will be compared as previously outlined^{65, 67, 68}. These representative sequences are aligned using PyNAST and taxonomy assigned to them using the RDP Classifier. The PyNAST-aligned sequences will also be used to build a phylogenetic tree with FastTree and unweighted UniFrac distances then computed between all samples for additional ecological analyses, including principal coordinates analysis (PCA)^{65–67}.

Adverse Event (AE) Reporting:

The subjects enrolled in this trial are initially critically ill subjects deemed to require both PN and prolonged ICU care. Such individuals are known to have a high morbidity and mortality rate. No AEs specifically due to the study nutrient formulations are expected. However, we will closely monitor the clinical course of all subjects daily and record conventional serious adverse events (SAEs) and unexpected and expected AEs, as well as note significant clinical or surgical events as narrative data. For the purposes of study reporting, an SAE is any of the events below:

1. Death
2. Re-hospitalization after study PN or tube feeding discontinuation
3. Documented pulmonary aspiration of study tube feeds during study tube feed administration
4. New cancer diagnosis
5. Congenital anomaly/disorder

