Data and Safety Monitoring Board (DSMB): The Data and Safety Monitoring Board (DSMB) will act in an advisory capacity to the National Institute of Diabetes, Digestive and Kidney Diseases (NIDDK) to monitor subject safety and evaluate the efficacy of the intervention being studied in this clinical trial funded by the NIDDK. The DSMB will be appointed by the PIs upon study funding, and approved by NIDDK program staff. The DSMB will be composed of at least two experienced clinical nutrition support investigators not otherwise participating in the study and not affiliated with Emory. A biostatistician not otherwise participating in the study will also be named to the DSMB. The DSMB will meet twice yearly, and as needed, and will receive blinded and unblinded reports on study progress prepared by the DCC.

Statistical Analysis:

Continuous variables will be summarized with standard descriptive statistics and represented graphically with displays such as scatterplots, box plots, line plots and histograms, while categorical variables (adverse events) will be described by frequency tables.

For Aim 1: The primary analyses of the data will be performed according to subjects' original treatment assignment (i.e., intention-to-treat analyses) and the inclusion of all data from all subjects randomized in the final analysis. Rates of infection (i.e., BSI and total nosocomial infections) per 1000 hospital days will be estimated overall and for each of the 3 energy doses. Confidence intervals (95%) for the incidence rates will be estimated using an exact method based on the Poisson distribution.

Additionally incidence rates of infection will be estimated by performing a generalized estimating equations (GEE) Poisson regression analysis of the counts, implemented using SAS Proc Genmod, using an exchangeable correlation structure for the repeated counts within subject. The incidence rate ratio (IRR) is the ratio of the incidence density in one group to that of another group. Results by each baseline covariate will be presented as the IRR and the 95% confidence interval (CI). This GEE model can also accommodate time-dependent covariates such as daily blood glucose levels measured before an infection and total 28-day energy (cumulative deficit or as a time-dependent covariate).

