Twenty-eight day mortality will be summarized as a proportion plus the 95% confidence interval (overall and for each treatment group). The 28-day mortality will be compared between treatment groups using a chi-square or Fisher's exact test. The potential association of each of the categorical prognostic factors (gender, race, high or low Apache score, clinical center) with mortality will also be evaluated using a Chi-square test or Fisher's exact test. Baseline continuous prognostic factors (age, SOFA score, blood glucose) will be compared by treatment group using the Wilcoxon rank-sum test. Odds ratios will be calculated to measure the degree of association. All statistical tests will be 2-sided. Factors significant to at least a value of $P \leq 0.20$ in the univariable analyses will be used in multivariable logistic regression analyses. Forward and backward stepwise selection will be used if necessary to choose prognostic variables for a multivariable logistic regression model. The odds ratio and its 95% confidence interval will be calculated for each factor in the presence of others in the final model.

Days on mechanical ventilation, length of ICU stay and hospital length of stay will be summarized with percentiles (25th, 50th and 75th) and the median absolute deviation. These secondary outcomes will be compared between the 3 treatment groups using the Kruskal-Wallis test. Repeated-measures analyses of daily SOFA scores and laboratory measures such as blood glucose will be analyzed with a means model with SAS Proc Mixed (version 9, mixed linear models) providing separate estimates of the means by time on study (days 0, 3, 7, 14, 21, and 28) and treatment group (energy dose: 0.6, 1.0 and 1.3 x REE). An unstructured variance-covariance form among the repeated measurements will be assumed for each outcome and estimates of the standard errors of parameters will be used to perform statistical tests and construct 95% confidence intervals. T-tests will be used to compare the pairwise differences between the model-based treatment means (least-squares means) at each time point. Statistical tests will be 2-sided. The model-based means are unbiased with unbalanced and missing data, so long as the missing data are non-informative (missing at random). A dropout process is assumed to be missing at random if; conditional on the observed data, the dropout is independent of the unobserved measurements.

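### Ventilator-free days are a listed secondary endpoint with no formula, death score or named test; the analysis section tests days on ventilation and raw stays instead, with no rule for deaths

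*Combined protocol and SAP*

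**What the plan says.** The Study Schema states that "secondary endpoints are bloodstream infections, ventilator-free days, and ICU and 28-day hospital length of stay and mortality". The endpoint list under Serial data entry via case report forms includes "ICU ventilator-free days at day 28; 6) ICU and total hospital length of stay". Together these give ventilator-free days a setting (ICU) and a horizon (day 28), but no formula, no score for a patient who dies and no rule for a return to ventilation.

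The Statistical Analysis section does not use the term. Its nearest text is the opening general sentence, "Continuous variables will be summarized with standard descriptive statistics and represented graphically", which supplies neither a test nor a death rule. Under Aim 1 it says: "Days on mechanical ventilation, length of ICU stay and hospital length of stay will be summarized with percentiles (25th, 50th and 75th". It then says: "These secondary outcomes will be compared between the 3 treatment groups using the Kruskal-Wallis test". By its position, that sentence refers to the three durations just named.

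The same section commits to "the inclusion of all data from all subjects randomized in the final analysis", so patients who die stay in these comparisons. Mortality is compared separately by chi-square or Fisher's exact test. The missing-at-random statement is attached to the mixed models for SOFA and laboratory values, not to the durations.

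The window for hospital stay is 28 days in the Study Schema, total stay in the endpoint list, and unstated in the Statistical Analysis.

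**The concern.** Days on mechanical ventilation and ventilator-free days are different measures. Ventilator-free days normally combine survival with time off the ventilator. Days on ventilation do not, and their meaning for a patient who dies depends on a rule that the plan lacks. The listed endpoint therefore has no planned test, while the tested variable has no planned treatment of death.

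The Adverse Event section expects high mortality in this population, so the gap will arise in practice. If days are simply counted to death, a patient who dies on the ventilator early ranks better than a survivor weaned later, and one who dies on it late ranks worse. Either way a difference in deaths can appear as a difference in duration. If the rule is chosen once the data are in hand, the choice can follow the result. The trial exists to inform later powered trials, so these medians may be used as design inputs.

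**Working it through.** The documents give no mortality, ventilation time, effect size or power for these endpoints, so there is no planned figure to reproduce. The check has two parts.

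**1. Worked example (assumed values).** Two arms of 20. Arm A has 8 deaths and arm B has 3. Every survivor is ventilated for 10 days, and those who die are ventilated until death.

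- Deaths on day 4, mean days on ventilation: A = (8×4 + 12×10)/20 = 152/20 = 7.6; B = (3×4 + 17×10)/20 = 182/20 = 9.1. The arm with more deaths looks better.
- Deaths on day 20, mean days on ventilation: A = (8×20 + 12×10)/20 = 280/20 = 14.0; B = (3×20 + 17×10)/20 = 230/20 = 11.5. The same arm now looks worse.
- Ventilator-free days to day 28 with death scored 0 (a survivor scores 28 − 10 = 18): A = 12×18/20 = 10.8; B = 17×18/20 = 15.3. This result does not depend on when the deaths occur.

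**2. Simulation.** From the documents: three arms of 20 and the Kruskal-Wallis test. Assumed: two-sided level 0.05; underlying ventilation time gamma with mean 12 days and shape 2, identical in all arms; all patients ventilated; days counted to death and capped at 28; mortality 10/10/30%; death times uniform within the stated window. Two models of death were used. In the first, death only truncates ventilation (days = the smaller of ventilation time and death time). In the second, those who die stay ventilated until death (days = death time). The table gives the share of trials in which the 30% arm has a lower median than one 10% arm (50% if there is no distortion), and the Kruskal-Wallis rejection rate.

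| Deaths on days | Truncation: lower median | Truncation: rejects | Ventilated to death: lower median | Ventilated to death: rejects |
|---|---|---|---|---|
| 1–9 | about 76% | 9% | about 73% | 9% |
| 4–14 | 64% | 6% | 55% | 5% |
| 4–28 | 57% | 5% | 37% | 6% |
| 7–28 | 53% | 5% | 32% | 7% |
| 14–28 | 50% | 5% | about 22% | 11% |

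- At equal mortality (20% in each arm) both models give about 50% and about 5%.
- If 25% of patients are never ventilated, the truncation shares fall to about 66%, 57% and 50% for deaths on days 1–9, 4–14 and 14–28.
- Ventilator-free days with death scored 0 have a lower mean in the 30% arm in about 87% of trials, and Kruskal-Wallis rejects in about 16–18%, with little dependence on death timing. For comparison, the planned mortality test rejects in about 38% by chi-square or about 30% by Fisher's exact test.

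**The case against.** A reader might infer that the plan systematically rewards an arm with more early deaths. The documents do not support that. They do not say that days are counted to death, and they give no mortality rate or timing. The Potential Risks section states that no data suggest mortality differs between the doses. Eligibility requires expected survival, with an ICU stay of at least 96 hours in the Study Procedures text and 72 hours in the inclusion criterion, which argues against the very earliest deaths. A favourable shift needs early deaths and clearly unequal mortality, and it shrinks if some patients are never ventilated. That stands.

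The opposite inference, that late deaths leave the comparison unbiased, fails too. It holds only if death merely truncates ventilation; if those who die stay ventilated until death, late deaths make the high-mortality arm look worse. The direction is unknown in advance.

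It can also be said that mortality is tested separately, that these are secondary endpoints of a pilot, and that a death-scored measure partly repeats the mortality test. All three are true and limit the importance of the point. Separate mortality reporting lets readers see the deaths but does not correct the duration comparisons, and it does not supply a test for the listed endpoint. Finally, worst-rank scoring of ICU and hospital stay is only one reasonable choice; treating death as a competing event, or reporting stays by survival status, could also serve.

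**Conclusion.** The specification gap holds on the text alone, whatever the mortality: a secondary endpoint listed in two places has no operational definition and no named test, and the durations tested in its place have no rule for deaths. The statistical consequence is conditional. It needs days counted to death and unequal mortality, and its direction depends on when deaths occur and whether those who die remain ventilated. At 10/10/30% mortality the share of trials with a lower median in the high-mortality arm runs from about 76% down to about 22%, against 50% with no distortion. Test rejection stays at about 4–11%, so the distortion shows more in the reported medians than in false rejections. With equal mortality there is little distortion. These sizes rest on assumed inputs, not on figures in the documents. The primary infection endpoint is not affected by this point. The change should be made, at modest priority.

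**What to change.** In the Aim 1 part of the Statistical Analysis:

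- Make ventilator-free days to day 28 the tested ventilation outcome, in the same Kruskal-Wallis test. Define it as 28 minus all days ventilated through day 28, with days after re-intubation counted as ventilated, and score it 0 for death by day 28.
- State whether the ICU qualifier in the endpoint list limits the count, and state an assumption for ventilation after hospital discharge (for example, ventilator-free if discharged alive off the ventilator).
- Report days on mechanical ventilation, ICU stay and hospital stay descriptively by survival status.
- Reconcile 28-day with total hospital stay. If the stays are still tested, pre-specify how deaths enter; worst rank is one option.
- Say whether the "28-day hospital mortality" of the endpoint list and the 28-day mortality of the analysis section are the same quantity, since the death score relies on it.

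The cost is a few sentences. Deaths to day 28 should already be captured for patients who start study feeding: death heads the list introduced by "For the purposes of study reporting, an SAE is any of the events below", and reporting runs to 30 days after study drug discontinuation. That route does not clearly cover a patient randomised but never fed. No section states that ventilation is recorded after hospital discharge, which is why an explicit assumption is needed. The downside is small: the death-scored measure partly re-detects mortality, so the durations by survival status should be shown beside it.

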Comparative effectiveness of energy doses in critical illness

Short title: The Energy Dose Study

Principal Investigator: [name].

Protocol Version Date: 6/2/2014

NCT Number: NCT01369147

Abstract:

Protein and/or energy deficits are associated with increased rates of hospital infection, skeletal muscle weakness, impaired wound healing, and prolonged convalescence in ICU patients. To prevent or treat malnutrition, enteral nutrition (EN) and/or parenteral nutrition (PN) are routinely given worldwide to a significant proportion of ICU patients. Optimal caloric requirements in critically ill patients are unknown due to a lack of rigorous randomized clinical trials. The comparative efficacy of energy doses in critically ill patients is unknown and clinical recommendations are conflicting and controversial; this issue is the focus of our study.

We have designed this pilot, single-center Randomized Clinical Trial (RCT) to prospectively compare, for the first time, the clinical efficacy of different energy doses in ICU patients requiring PN due to intestinal failure/dysfunction. A total of 60 patients will be studied (20 per energy dose group) to generate critical preliminary data needed to inform subsequent appropriately powered Phase III multicenter trials.

The primary aim of this study is to perform a controlled, double-blind, prospective, randomized, intent-to-treat Phase II clinical trial to test the efficacy of three specific energy doses [0.6, 1.0 and 1.3 x measured REE (resting energy expenditure), respectively], given for 28 consecutive days during the ICU course, on 28-day total hospital-acquired infections (primary endpoint), Blood Stream Infections (BSI), and other important clinical outcomes in medical/surgical ICU patients requiring specialized parenteral \pm enteral feeding. We would also determine, in these subjects A) the impact of cumulative and mean daily 28-day energy deficits [energy intake-measured REE] on clinical outcome endpoints; and B) the practical utility of estimated REE determined by Harris-Benedict equation versus measured REE across different energy doses. We would also like to determine the impact of administered energy dose and energy deficits on global metabolomic patterns over time and their association with key clinical outcomes.

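### Later SOFA and glucose arm differences are not baseline-adjusted, because day 0 is fitted as a response with a free mean in each arm; the variance given up is about the squared correlation with day 0

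*Combined protocol and SAP*

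**What the plan says.** Statistical Analysis, For Aim 1, plans a mixed linear model in SAS for the repeated SOFA and glucose values. Its mean structure has one free cell for each arm at each visit, described as "providing separate estimates of the means by time on study (days 0, 3, 7, 14, 21, and 28) and treatment group". For the covariance, "An unstructured variance-covariance form among the repeated measurements will be assumed for each outcome". The arm comparison is by visit: "T-tests will be used to compare the pairwise differences between the model-based treatment means (least-squares means) at each time point".

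For these two outcomes the plan names no baseline covariate, no common day-0 mean and no change-from-baseline contrast. The same section calls baseline SOFA and glucose prognostic factors, but only compares them between arms with a Wilcoxon test. Randomization of study subjects stratifies by clinical center and by APACHE II score (15 or below, above 15); neither factor is named in this model.

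The sample size is given in the Abstract: "A total of 60 patients will be studied (20 per energy dose group"). Data Collection, item B, has SOFA scored on ICU days only.

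**The concern.** In a randomised trial, the arms share one true mean before treatment starts. A model that gives each arm its own day-0 mean does not use that fact. Whatever chance difference exists at day 0 is absorbed by the day-0 parameters, and the part of it that persists stays in the later arm differences.

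With 20 patients per arm such chance differences are not small. Under normality and ignoring stratification, the largest day-0 gap among the three arms exceeds 0.5 SD with probability of about 25%. Stratifying by APACHE II should reduce this somewhat for SOFA.

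What is at stake is the precision of secondary results. Mean ICU SOFA is a listed secondary endpoint, and the trial exists to supply estimates for later Phase III trials. The day-0 values are already collected, so any precision they could add comes without extra patients.

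Testing at each time point also includes day 0, where a comparison of randomised arms can show only chance.

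**Working it through.** **Inputs.** From the documents: three arms, 60/3 = 20 patients per arm; visits at days 0, 3, 7, 14, 21 and 28; a free mean for each arm and visit; unstructured covariance; two-sided tests. The documents give no SD, no correlation between visits, no effect size and no precision target for SOFA or glucose, so there is no planned figure to reproduce. Rho and the retention pattern below are assumptions.

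**Variance of an arm difference at one visit, complete data, in SD² units.**

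- As planned: 2/n = 2/20 = 0.100, so SE = 0.316 SD. With complete data and a free mean in every cell, the model estimate equals the raw mean difference. Deleting day 0 from the model leaves this variance at 0.100.
- With a common day-0 mean, or day 0 as a covariate: (2/n)(1 − rho²).
- Share of variance given up: rho².

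| rho (assumed) | variance given up | SE with adjustment (SD) | equivalent n per arm, 20/(1 − rho²) |
|---|---|---|---|
| 0.2 | 4% | 0.310 | 20.8 |
| 0.3 | 9% | 0.302 | 22.0 |
| 0.5 | 25% | 0.274 | 26.7 |
| 0.7 | 49% | 0.226 | 39.2 |

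On the SE scale, rho of 0.5 to 0.7 means an SE 13% to 29% smaller.

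**Cost of estimating the slope.** With 60 patients, three arm means and one covariate, the variance inflation is about 1/(60 − 3 − 2) = 1/55 = 1.8%. Net gains are then about 2% at rho 0.2, 7% at 0.3, 24% at 0.5 and 48% at 0.7. Adjustment breaks even where (1 − rho²)(56/55) = 1, that is, at rho of about 0.13.

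**If the correlation decays with time.** Let rho = k^(days/7). Then rho² at each visit, complete data, is:

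| k per week (assumed) | day 3 | day 7 | day 14 | day 21 | day 28 |
|---|---|---|---|---|---|
| 0.5 | 55% | 25% | 6% | 2% | 0.4% |
| 0.7 | 74% | 49% | 24% | 12% | 6% |

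**If values are missing.** Assume 20, 19, 17, 13, 10 and 8 patients per arm remain at the six visits, with monotone loss at random. Generalised least squares with known covariance and a constant rho gives these losses against the model with a common day-0 mean:

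| rho (assumed) | loss at day 3 | loss at day 28 |
|---|---|---|
| 0.3 | 9% | 4% |
| 0.5 | 24% | 13% |
| 0.7 | 48% | 31% |

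Here day 0 does contribute to the planned model through the covariance, but it lowers the variance by at most about 4% compared with leaving day 0 out.

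**Illustration of power.** For a true difference of 0.8 SD (assumed), two-sided 0.05 and complete data, power is 0.72 as planned, 0.76 with adjustment at rho 0.3, 0.83 at 0.5 and 0.94 at 0.7.

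**The case against.** Three stronger readings are tempting, and the documents support none of them.

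- **A reader might infer that the plan gives up a quarter to a half of the attainable precision.** That needs rho of about 0.50 to 0.71, held constant to day 28, with complete data. No correlation is given, and lower or decaying values are plausible. For glucose, Clinical management guidelines has staff steering values toward common targets, which could weaken the link to day 0. SOFA stops at ICU discharge, and the expected ICU stay at entry is only 72 hours in the inclusion criteria (96 in the paragraph before), so late visits will have fewer values.
- **A reader might infer that day 0 is not used at all.** It is in the response vector with an unstructured covariance, and it informs later means when values are missing. The plan relies on this: "The model-based means are unbiased with unbalanced and missing data, so long as the missing data are non-informative (missing at random"). The contribution is small in the check above, but it is not zero.
- **A reader might infer that the planned comparison is biased.** It is not. Under randomisation the unadjusted differences are unbiased, and their standard errors already allow for chance imbalance.

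It is also fair to say that this is a 60-patient pilot with infection as its primary endpoint, that the listed secondary endpoint is the mean ICU SOFA score rather than SOFA at each visit, and that glucose is not a listed endpoint. All of this stands and limits the importance of the point. None of it supplies a baseline adjustment: the Wilcoxon comparison does not adjust these contrasts, and the change-from-baseline wording at the end of the section concerns the microbiome only.

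**Conclusion.** The point holds as one of efficiency. As written, the SOFA and glucose arm differences at days 3 to 28 are not baseline-adjusted, and this costs about rho² of the variance at each visit with complete data: 4% at rho 0.2, 9% at 0.3, 25% at 0.5, 49% at 0.7. The structure is certain from the text; the size is not, because rho is an assumption throughout. The gain is likely to be greatest at day 3. It could be negligible by day 28, and missing values shrink it further at late visits. Below rho of about 0.13 there is no gain, and the most that adjustment can then cost is about 2% of variance. Validity and the primary analysis are not in question.

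**What to change.** Keep the Proc Mixed model and the unstructured covariance, and change the mean model:

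1. Constrain the day-0 mean to be equal across arms, with arm-by-visit effects from day 3 on only. Alternatively, move day 0 to the covariate side with a visit interaction.
2. Add the randomisation strata: APACHE II 15 or below versus above 15, and hospital. Their extra gain beyond day 0 is not quantified here; the reason to include them is that the randomisation used them.
3. Compare arms only at days 3, 7, 14, 21 and 28, and drop the day-0 test.
4. State that the day-0 value is taken before study feeding begins, since the equality of means rests on this. The text points that way (baseline is day 0, and intake is recorded from day 1) but does not say it for SOFA and glucose.

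The cost is a changed model statement and a sentence or two in the analysis section, settled before unblinding. It needs no new data and no more patients. Label: free improvement.
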